COMMITTEES ON RESEARCH INVOLVING HUMAN SUBJECTS Established 1971

Protocol Summary Form

TITLE: Advancing Personalized Antidepressant Treatment Using PET/MRI **INVESTIGATORS:** [name] Co-Investigators: [name], PhD, [name], [name], [name], [name], [name], [name] [name], [name], PhD, [name], PhD **Department**: Psychiatry

A. SPECIFIC AIMS:

Despite the burden of failed trials, there are currently no tools for treatment selection in Major Depressive Disorder (MDD). Referring to a recent Positron Emission Tomography (PET) study using 2-[¹⁸F]-fluorodeoxyglucose (FDG), NIMH Director [name] remarked that PET imaging is "on the cusp" of aiding in MDD treatment decisions. To finally realize this goal, the limitations of previous FDG studies must be addressed, including limited sample size, lack of placebo comparison (the placebo effect is a significant obstacle to evaluating treatment mechanism and efficacy), and use of relative outcome measures. In the proposed study, FDG imaging before and after Selective Serotonin Reuptake Inhibitor (SSRI) treatment will be performed using a simultaneous PET/Magnetic Resonance (MR) scanner and: (1) the largest sample size to date; (2) a placebo group; and (3) full quantification using analysis of FDG activity in plasma, which yields more accurate estimates of metabolism than relative activity.

Aim 1: Determine a Pretreatment Marker of SSRI Effectiveness Using PET. With the goal of reducing MDD burden, many studies have assessed the utility of FDG-PET in antidepressant treatment prediction. However, due to the limitations listed above, there is no consensus on which brain regions are predictive of treatment efficacy. In addition to serving as a biomarker of SSRI effectiveness, only conclusive determination of these regions will provide insight into depression pathophysiology, helping uncover SSRI mechanism of action, and aiding in the search of novel therapeutics. Based on our preliminary data and other, similar studies, we hypothesize that SSRI-induced change in the Hamilton Depression Rating Scale (Δ HDRS) will be correlated with pretreatment metabolic rate of glucose (MRGlu, quantified using arterial blood analysis) in three potential regions: (1) midbrain, (2) right anterior insula, and/or (3) left ventral prefrontal cortex.

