Simultaneous Estimation Anchor: SimE has been recognized as a promising approach for noninvasive PET, as it works for several tracers used in neuroreceptor studies. By itself, however, SimE does not obviate the need to draw blood during the scan. To ensure model identifiability, at least one blood sample must be taken and used as an individual. We hope to be able to eliminate this single blood draw, which would help reduce barriers to widespread PET use.

C. RESEARCH DESIGN AND METHODS

1. Research Site

The PET/MRI scans will be performed at the Imaging Center (Ambulatory Care Pavilion) at the Stony Brook University Hospital.

2. Study sample

N = 120 (diagnosed with MDD) will be enrolled to obtain 100 subjects who complete the protocol

Age range: 18 years and above.

We anticipate the sample will comprise approximately equal numbers of males and females. No ethnic/racial/gender group is excluded.

3. Recruitment Methods

 Advertisements (flyers, brochures): Subjects will be recruited through response to advertisements, including local newspapers, on Craigslist and other websites. Approved fliers will be distributed around Stony Brook campus, other campuses, off campus locations such as health fairs and places of worship (with permission), and via letters from OPD to patients on their waitlist. Texts of advertisements and other materials to be distributed in recruitment efforts will be submitted to the IRB for approval before they are prepared for distribution. The use of websites and newspapers will allow us to target a broader range of the population.

- 2. Subjects will be recruited through lists obtained from the electronic medical record and provided to the study team by Research Services. The information we will receive for each patient include: MRN, patient age, name of treating physicians/nurses, date of most recent encounters, prescribed medication, diagnostic code with its corresponding official description and a free text description. Our study coordinators and clinician will have access to the data. Our team would contact the treating physician of potential participants through letter or telephone call. We will then ask the treating physician to provide information about our study to the patient, or ask the patient if we may contact him or her with more information.

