Image Processing: After MRI and PET processing is performed, the data will be processed using the semi-automated analysis pipeline developed in CUBIT. MRI processing includes segmentation (grey, white, csf) and parcellation into different regions of interest. PET processing includes motion correction, coregistration to the MRI, determination of regional activity over time (time activity curves) and modeling of the time activity curves. The modeling requires information about the radioactivity of plasma during the scan. These techniques have been previously described. (Parsey, Ogden et al. 2010, Miller, Hesselgrave et al. 2013) Using this analysis, the metabolic rate of glucose (MRGlu) can be calculated. The arterial input function (as well as Simultaneous Estimation, for comparison) will be used to derive the regional MRGlu.

E. STATISTICS

Aim 1: Correlation between HDRS and pretreatment MRglu will be determined in the ESC and placebo treatment groups in the three specified regions. In post hoc analysis, spatial resolution will be improved through examination of correlation between whole brain voxel MRglu and HDRS using SPM8 on aligned voxel based parametric images. Our group has extensive experience performing these analyses. For both analyses, outcome possibilities include: differential treatment Δ HDRS prediction (i.e. significant correlation, with different sign for placebo and ESC; significant correlation, within different regions, for placebo and ESC; significant correlation in same region, same direction); or insignificant correlation with HDRS for both treatments. The former outcomes would be immediately clinically significant and applicable. The final option, though unlikely based on preliminary data, would also be an important finding and suggest that, either the cohort should be expanded, or additional imaging/clinical measures are needed for prediction.

The power analysis was performed with an estimated 50 subjects per treatment. With a cohort of 50 subjects (on SSRIs), we can detect a true correlation as low as 0.39, with 80% power (two-tailed analysis, Δ = 0.05). In our FDG treatment study, the observed R2 value was 0.32, meaning the true correlation between the data was 0.57 (significantly higher than 0.39). However, this is almost certainly an overestimation because only the voxel cluster highly correlated to the outcome was chosen (as in all cited studies).

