Aim 2: The change in MRgIu from pre to post treatment (SSRI and placebo) will be calculated in the midbrain cluster defined by our preliminary studies. The correlation between this value and Δ HDRS will be assessed with both SSRI and placebo groups as well as with separate cohorts, to determine if there is an effect of treatment. As with Aim 1, a post hoc analysis will also be performed examining this correlation over all voxels.

Power Analysis. The partial correlation for each cluster and the factor related to "loss" varies between 0.5 and 0.6, meaning the true correlation ranges between 0.71 and 0.77. Based on this, using a single cohort (n=50), a true correlation as low as 0.39 can be detected with 80% power (two-tailed analysis, Δ =0.05).

When cohorts are combined (n=100 completers, of 120 enrollees), a correlation as low as 0.27 can be detected.

Aim 3: In a previous cohort, we investigated SimE performance with FDG (and four other tracers). The optimal timing for the blood sample used to anchor the FDG SimE estimation was found to be 40 minutes after injection. At this time, FDG venous and arterial samples are essentially interchangeable. Results using this 40-minute blood-based anchor show that SimE-derived MRGlu are close to MRGlu derived using arterial sampling-based estimation: slope 0.730, correlation 0.955 with compartmental analysis slope 0.876, correlation 0.974 with Patlak analysis. Validation: Validation will be considered complete when MRGlu using conventional (Patlak) analysis and arterial samples matches MRGlu calculated with SimE and one venous sample in the proposed study data. The threshold will be a correlation of at least 0.95 and slope of 0.85 in at least 30 subjects.

F. FUNDING STATUS

This study will be funded through the National Institute of Mental Health (R01MH104512-01A1; 1123782-1-70976), the DANA Foundation (Coeus Proposal #20458, PN15125265; 1128493-1-73073), the Brain and Behavior Research Foundation, (Grant #24459; 1134680-1-75849), internal funding from the Department of Computer Science and pilot funding provided by the Department of Radiology for PET/MRI scan costs.

G. DATA and SAFETY MONITORING PLAN (for more than minimal risk studies)

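### Aim 1's unadjusted correlation of absolute MRGlu with Δ HDRS cannot separate a metabolic marker from an age or sex effect; a prespecified adjustment is a cheap improvement

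*Combined protocol and SAP*

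**What the plan says.** Section E, Aim 1, gives the analysis in one sentence: "Correlation between HDRS and pretreatment MRglu will be determined in the ESC and placebo treatment groups in the three specified regions". The hypothesis in section A, Aim 1, makes clear that the outcome is change in HDRS, which "will be correlated with pretreatment metabolic rate of glucose (MRGlu, quantified using arterial blood analysis) in three potential regions". No covariate, partial correlation or regression model is named for this test or for the whole-brain voxel analysis that follows it, and section E never mentions age or sex.

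MRGlu is to be fully quantified from plasma, "which yields more accurate estimates of metabolism than relative activity" (section A). Section C.2 sets "Age range: 18 years and above", with no upper limit, and adds: "We anticipate the sample will comprise approximately equal numbers of males and females".

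On sample size, section E states: "The power analysis was performed with an estimated 50 subjects per treatment". With 50 subjects on SSRIs, "we can detect a true correlation as low as 0.39, with 80% power", two-tailed at 0.05 (the alpha symbol is printed as Δ).

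**The concern.** An absolute measure keeps all between-person differences in brain metabolism, including any due to age or sex. If those differences are unrelated to outcome, they add noise to the predictor and weaken the correlation. If they are related to outcome, they shift the correlation towards or away from zero. Randomisation does not help: it balances age between arms, but the marker–outcome relation within an arm is observational.

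This matters because of what Aim 1 wants to conclude. Section A expects the regions found to inform pathophysiology and how SSRIs work, and section E treats a positive result as ready for clinical use. A region that only tracks age would support neither, and would not justify PET with an arterial line, since age and sex are already known. There is also little room for attenuation. The design reaches 80% power only at about 0.39, and section E itself says that the preliminary correlation of 0.57 is probably too high.

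**Working it through.** **Inputs from the documents.** n = 50 per arm; two-sided alpha 0.05; detectable correlation 0.39 at 80% power.

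**Assumed inputs, not in the documents.** a = |corr(age, MRGlu)|, taken as 0.2 to 0.5; b = |corr(age, Δ HDRS)|, taken as 0 to 0.3; partial correlation p of MRGlu with Δ HDRS given age, taken as 0.39 or 0.

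**1. The plan's own figure.** By Fisher z, detectable r = tanh((1.960 + 0.842)/√(n − 3)) = tanh(2.802/√47) = 0.387. Power at 0.39 is Φ(atanh(0.39)·√47 − 1.960) = Φ(2.823 − 1.960) = 80.6%. The stated 0.39 reproduces.

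**2. What the raw test sees.** The raw correlation is r = p·√((1 − a²)(1 − b²)) ± ab. The sign is minus when age masks the marker and plus when age acts in the marker's direction. Example with a = 0.4, b = 0.2: 0.39 × √(0.84 × 0.96) = 0.350, so r = 0.350 − 0.080 = 0.270 (power 47.6%) or 0.350 + 0.080 = 0.430 (power 88.4%).

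Raw-test power, p = 0.39:

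| a | b = 0 | b = 0.2, masking | b = 0.2, same direction |
|---|---|---|---|
| 0.2 | 78.8% | 66.4% | 85.6% |
| 0.3 | 76.4% | 57.8% | 87.4% |
| 0.4 | 72.7% | 47.6% | 88.4% |
| 0.5 | 67.4% | 36.4% | 88.5% |

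**3. No marker beyond age (p = 0).** The raw correlation is then ab. Rejection rate of the raw test:

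| a | b = 0 | b = 0.1 | b = 0.2 | b = 0.3 |
|---|---|---|---|---|
| 0.2 | 5.0% | 5.2% | 5.9% | 7.0% |
| 0.3 | 5.0% | 5.5% | 7.0% | 9.5% |
| 0.4 | 5.0% | 5.9% | 8.5% | 13.1% |
| 0.5 | 5.0% | 6.4% | 10.6% | 17.9% |

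It is also 5% for any b when a = 0.

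**4. After adjusting for age and sex.** Two covariates replace n − 3 = 47 by 45. Power at p = 0.39 is Φ(0.4118 × √45 − 1.960) = Φ(0.802) = 78.9%, whatever a and b are. Detectable partial r = tanh(2.802/√45) = 0.395. The rejection rate at p = 0 is 5%.

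**5. Simulation check.** With 20,000 runs per case, and sex included as a covariate but given no effect:

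| p | a | b | Raw | Adjusted |
|---|---|---|---|---|
| 0.39 | 0.4 | 0 | 73.1% | 79.5% |
| 0.39 | 0.4 | 0.2, masking | 48.3% | 79.6% |
| 0 | 0.4 | 0.3 | 13.7% | 4.8% |

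These agree with the formulas to within about one point.

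**The case against.** The strongest reply is that Aim 1 hypothesises a plain association. If age makes the raw correlation non-zero, the stated null is false, and rejecting it is not an error of the planned test. That is right. A reader might infer that the planned test has an inflated type I error; the documents do not support this. The rates in step 3 are error rates only for a different question, whether MRGlu adds to age. That question still matters, because the claims about mechanism and clinical use depend on it.

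Second, 0.39 in section E is a raw correlation, and at a raw 0.39 the planned test has its stated power. The comparison in step 2 sets the partial correlation at 0.39 instead. This also stands: the power statement is not wrong for the test it describes.

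Third, a reader might infer that adjustment always restores power. It does not. Where age acts with the marker, raw power is 86–89% and adjustment lowers it to about 79%, because part of the raw signal was age.

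Fourth, a and b are both outside the documents. With weak links the effect is small, and the 18% needs the most extreme pair in the table. For sex there is no figure at all; it enters only as a second covariate.

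Finally, section E, Aim 2, cites earlier work with the words "The partial correlation for each cluster". A reader might infer that the team formerly adjusted for age and sex and has dropped it here. The variables adjusted for are not named, so the passage does not show that.

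**Conclusion.** The point holds as a cheap improvement, not as proof that the planned test is miscalibrated. The plan leaves age and sex out of a test on an absolute measure in adults of any age, so a positive Aim 1 result could not be read as a metabolic marker over and above age and sex.

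How much this matters cannot be fixed from the documents. Over the assumed range it runs from negligible (5–6% rejection without a marker beyond age at a = 0.2, b = 0.1–0.2) to serious (masked power of 36% at a = 0.5, b = 0.2). The recommendation does not depend on one value: adjusting when age is irrelevant costs 1.7 points of power, while omitting it when age masks the marker can cost tens of points. The calculation assumes linear age effects and 50 completers per arm. It leaves aside the separate question of testing three regions in two arms.

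**What to change.** In section E, Aim 1, state that each regional test is the partial correlation (or regression slope) of Δ HDRS on pretreatment MRGlu adjusted for age and sex, fixed in advance and identical in both arms, with the unadjusted correlation reported beside it. Restate the detectable value as a partial correlation of about 0.40.

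The cost is the wording and two degrees of freedom: power at 0.39 goes from 80.6% to 78.9%, and the detectable value from 0.387 to 0.395. No new data are needed, since age is an eligibility item and sex must be known for the pregnancy criterion.

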Despite current medications, morbidity and mortality of Major Depressive Disorder (MDD) remain high. (Benton, Staab et al. 2007) According to the World Health Organization, MDD affects 121 million people worldwide, and is projected to be the second leading cause of global disability by 2020. Monotherapy with SSRIs is the most widely used treatment for MDD. (Leuchter, Lesser et al. 2008) However, on average, SSRIs require six weeks for onset of action, and two-thirds of those on SSRIs fail to achieve remission.(Trivedi, Rush et al. 2006, Leuchter, Cook et al. 2010) Compounding this problem, patients with residual symptoms are significantly more likely to discontinue treatment or relapse, be hospitalized for medical and psychiatric conditions, or die of suicide and other causes.(Trivedi 2003, Trivedi, Rush et al. 2006, Warden, Trivedi et al. 2007) Although eliminating ineffective treatment trials would significantly reduce patient suffering and healthcare costs, (Taylor, Youngblood et al. 2005, Leuchter, Cook et al. 2010) clinicians currently do not have the tools to objectively select treatment based on an individual's likelihood of remission. Therefore, there is an urgent need to identify markers predictive of an individual's SSRI treatment outcome (Taylor, Youngblood et al. 2005, Leuchter, Cook et al. 2010). Developing this personalized treatment requires increased understanding of the relationship between pretreatment neurobiology, SSRI-induced biological changes, and the corresponding symptom improvements.

Our proposed study, in which FDG-PET scans are acquired before and after escitalopram (or placebo) treatment, avoids these previous limitations by standardizing treatment across all subjects, enrolling 120 subjects to ensure that at least 100 will complete the protocol (largest sample size to date), performing full quantification with arterial blood sampling, and a priori defining the clinical outcome measure as Δ HRDS. Further, we will uncover neurobiological correlates of pathophysiology that span diagnoses.

Potential Noninvasive Estimation: PET research/clinical laboratories have differing levels of software and/or hardware expertise. The key, therefore, to promoting widespread PET use is to develop multiple, validated pathways for noninvasive imaging. In this study, we will evaluate Simultaneous Estimation.

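### Aim 1 treats patterns of within-arm significance as differential prediction, with no between-arm test and no between-arm power

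*Combined protocol and SAP*

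**What the plan says.** Section A, Aim 1 hypothesises that "SSRI-induced change in the Hamilton Depression Rating Scale (Δ HDRS) will be correlated with pretreatment metabolic rate of glucose" in up to three regions joined by and/or. Section A also lists, among the limitations of past FDG studies that must be addressed, "lack of placebo comparison (the placebo effect is a significant obstacle to evaluating treatment mechanism and efficacy". Section B sets the outcome by "a priori defining the clinical outcome measure as Δ HRDS".

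Section E, Aim 1 says that the correlation with "pretreatment MRglu will be determined in the ESC and placebo treatment groups in the three specified regions". It then lists possible outcomes. Under differential prediction it places opposite signs in the two arms, followed by "significant correlation, within different regions, for placebo and ESC; significant correlation in same region, same direction". The remaining possibility is no significant correlation in either arm. Of everything before that last option it says: "The former outcomes would be immediately clinically significant and applicable".

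The power statement is: "With a cohort of 50 subjects (on SSRIs), we can detect a true correlation as low as 0.39, with 80% power". No power is given for a difference between arms. Aim 2 does not fill the gap. It examines the arms pooled "as well as with separate cohorts, to determine if there is an effect of treatment", and its n = 100 figure (0.27) is for a pooled correlation.

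**The concern.** A differential claim concerns the difference between two correlations. The plan offers two separate tests against zero and compares their verdicts. One arm can be significant and the other not although both share the same true correlation. A marker that works equally well in both arms predicts improvement on placebo too, so it cannot by itself show who benefits from the drug.

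The trial is presented as a step towards choosing treatment for individual patients, and the placebo arm as the remedy for a known weakness of earlier work. Followed as written, the list lets a general prognostic marker, or a chance difference in which regions reach significance, be reported as differential and ready for clinical use. Readers also cannot tell how well 50 per arm can detect a real difference between arms.

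**Working it through.** **Inputs from Section E, Aim 1.** 50 completers per arm; two-sided 0.05 (printed with a Δ, read as alpha); detectable r = 0.39; preliminary r = √0.32 = 0.57, which the plan itself calls an overestimate. **Assumptions, not in the documents.** The placebo correlation, the correlation between regions, and a second common value r = 0.30.

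**1. The plan's own figure.** Detectable r = tanh((1.960 + 0.842)/√47) = tanh(0.409) = 0.387. Power at 0.39: atanh(0.39) × √47 = 0.4118 × 6.856 = 2.823, and Φ(2.823 − 1.960) = 80.6%. The 0.39 reproduces for one region in one arm.

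**2. The same figure over three regions.** No multiplicity control is stated. Familywise error is 1 − 0.95³ = 14.3% if the regions are independent (12.6% if they correlate 0.5). With Bonferroni (0.0167, critical value 2.394), power at 0.39 is Φ(2.823 − 2.394) = 66.6%.

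**3. Opposite signs, both significant in one region.** The critical |r| at n = 50 is 0.279. Two results just at that limit differ by 2 × atanh(0.279) = 0.573. The standard error of a Fisher-z difference is √(1/47 + 1/47) = 0.206, so z = 2.78 and p is about 0.006. This pattern does support a difference.

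**4. Different regions.** Let the true correlation be equal in both arms. The chance p of significance in one arm is 0.806 at r = 0.39 and 0.564 at r = 0.30. Exactly one arm is significant in a given region with probability 2p(1 − p) = 31% and 49%. Over three regions there are two readings, both requiring each arm to have at least one significant region. Strict: no region is shared. Loose: the two sets of regions are not identical.

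| Assumption | Strict, r = 0.39 / 0.30 | Loose, r = 0.39 / 0.30 |
|---|---|---|
| Three true regions, independent | 3% / 16% | 66% / 72% |
| Three true regions, correlated 0.5 (simulated) | 2% / 8% | about 52% / 54% |
| One true region, two null, independent | 3% / 5% | 15% / 11% |

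The independent rows enumerate all 64 significance patterns.

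**5. Same region, same direction.** With a common true r, both arms are significant in a given region with probability p² = 65% at 0.39 and 32% at 0.30. This is the power to detect a shared correlation that really exists. The error lies in calling the result differential.

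**6. Between-arm power at 50 per arm.** Power is Φ(d/0.206 − c), where d is the difference in Fisher z and c is 1.960 or 2.394 (the opposite tail is negligible except in the first row, where it is included). For 0.39 against 0, d/0.206 = 0.4118/0.2063 = 1.996 and Φ(0.036) = 51%.

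| ESC r | Placebo r | d/0.206 | Alpha 0.05 | Alpha 0.0167 |
|---|---|---|---|---|
| 0.39 | +0.2 | 1.01 | 17% | 8% |
| 0.39 | 0 | 2.00 | 51% | 35% |
| 0.39 | −0.2 | 2.98 | 85% | 72% |
| 0.57 | +0.2 | 2.16 | 58% | 41% |
| 0.57 | 0 | 3.14 | 88% | 77% |

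For 80% power against placebo r = 0, the ESC correlation must be tanh(2.802 × 0.2063) = 0.52, or 0.58 at alpha 0.0167. Detecting 0.39 against 0 at alpha 0.05 needs 2 × 2.802²/0.4118² + 3, about 96 completers per arm. A regression with an arm-by-MRGlu term, simulated with equal SDs in both arms, gave nearly the same power (51% for 0.39 against 0 at alpha 0.05), so these figures carry over to the proposed test.

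**The case against.** The strongest reply is that the text introduces its list as possibilities. It is an open, grant-style set of interpretations, and the hypothesis in Section A is a correlation under SSRI that needs no comparison of arms. One listed pattern is sound, and the third may sit inside the differential bracket only through a slip of punctuation. A marker common to both arms could still be useful for prognosis.

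Part of this stands. The list is not a formal decision rule, and the single-region ESC correlation is a valid 0.05 test. However, the sentence on clinical applicability covers every pattern except the null one, so moving the third pattern outside the bracket does not help. The plan also offers no other analysis on which a differential claim could rest.

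Three stronger inferences are tempting and are not supported. First, a reader might take 65% and 32% as false-positive rates; they are joint power for a true shared effect. Second, a reader might conclude that a different-regions result would usually arise by chance. That depends on the loose reading with three true regions. On the strict reading it is 2% to 3% at r = 0.39 and 5% to 16% at r = 0.30. Third, a reader might infer that the differential question cannot be answered at this size. At the plan's own 0.57 against placebo 0, power is 88% (77% at alpha 0.0167), although the plan discounts that value.

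**Conclusion.** The concern holds in a limited form. Aim 1 labels within-arm significance patterns as differential and clinically applicable without a between-arm test or between-arm power. Two of the three patterns do not support the label; opposite signs, both significant in one region, do.

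The reproduction of 0.39 might be read as clearing the within-ESC hypothesis as a whole. It does not. That hypothesis can be met by any of three regions with no stated alpha control, and a correlation in the ESC arm alone cannot separate SSRI-induced change from placebo response.

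Between-arm power runs from 17% to 88% at alpha 0.05 and from 8% to 77% at 0.0167 over the cases shown. These figures assume 50 completers per arm, approximate normality, and placebo correlations that the documents do not give. The chance of a different-regions result also depends on assumed inter-region correlations and on how many regions are truly related to outcome. The point should be settled before analysis, because it governs what the trial may claim about treatment selection.

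**What to change.** For each of the three regions, fit week-8 HDRS change on arm, pretreatment MRGlu and their product, using both arms together. HDRS change is the plan's own a priori outcome, although the Aim 1 analysis sentence names only HDRS and should be aligned. Week 8 is the last point before the blind is broken and while both arms are on assigned treatment (Section D). Apply Holm over the three interaction tests, and report the ESC and placebo slopes with confidence intervals.

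In the text:
- Base any differential or treatment-selection claim on the interaction.
- Reclassify a shared region with the same sign as a prognostic outcome.
- Do not read significance in different regions as differential without a supporting interaction.
- Label 0.39 at 80% power as the single-region, within-ESC figure at alpha 0.05, and state how the three within-ESC tests are handled for multiplicity.
- Give between-arm power for ESC correlations from 0.39 to 0.57 over a range of placebo correlations, at the adjusted alpha.

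Keep the within-ESC correlation as the analysis of the stated hypothesis. Adjustment for baseline HDRS is an optional gain in precision.

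The cost is revised wording, one model term and a less favourable power statement. The differential question may prove inconclusive at this size, and the plan would have to say so. No new data or visits are needed.

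### Aim 1 treats patterns of significant correlation as clinically applicable, but p<0.05 with 50 subjects per arm is compatible with weak individual prediction, and no predictive measure is planned

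*Combined protocol and SAP*

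**What the plan says.** The Background (section B) sets the purpose: "clinicians currently do not have the tools to objectively select treatment" according to a given patient's chance of remission, and markers of individual SSRI outcome are needed.

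Section E, Aim 1 plans correlations between pretreatment MRGlu and HDRS in each arm, in three specified regions, followed by a post hoc whole-brain voxel analysis. For both analyses it lists the possible results. Three are significant: opposite signs in the two arms, different regions in the two arms, or the same region and direction in both. The last is no significant correlation in either arm. Of the significant ones it says: "The former outcomes would be immediately clinically significant and applicable".

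The power paragraph that follows states: "With a cohort of 50 subjects (on SSRIs), we can detect a true correlation as low as 0.39, with 80% power" ("two-tailed analysis, Δ = 0.05", where the symbol is evidently alpha). It cites earlier data in which "the observed R2 value was 0.32, meaning the true correlation between the data was 0.57", and adds that "this is almost certainly an overestimation because only the voxel cluster highly correlated to the outcome was chosen".

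For Aim 1 the documents give no minimum r or R2, prediction error, discrimination measure, cross-validation, validation in new subjects, or treatment-by-marker interaction. Aim 3, by contrast, sets performance thresholds before validation is complete: correlation of at least 0.95 and slope of 0.85, in at least 30 subjects.

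**The concern.** A test of a correlation asks whether the slope differs from zero in a group. Choosing a treatment for one patient requires knowing how closely that patient's outcome can be predicted, and whether the prediction differs between treatments. The Aim 1 text goes from the first question to a claim about the second with nothing in between. This is separate from the multiplicity of regions and from the voxel search: it would remain for one pre-specified region with a valid test.

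At stake is the wording of the trial's conclusion. A marker with little value for an individual decision could be reported, in line with the plan, as ready for clinical use.

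**Working it through.** **Inputs.** From section E, Aim 1: n = 50 per arm, two-sided alpha 0.05, power 80%, detectable r = 0.39, preliminary r = 0.57 (R2 0.32). From section B: about one third of SSRI patients remit. Assumed: MRGlu and Δ HDRS are bivariate normal.

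**1. The plan's own figure.** By Fisher's z, detectable r = tanh[(1.960 + 0.842)/√(50 − 3)] = tanh(0.409) = 0.387. The stated 0.39 is reproduced; power at 0.39 is 80.6%.

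**2. Smallest significant observed r.** With t(0.975, 48 df) = 2.011, r = t/√(n − 2 + t²) = 2.011/√(48 + 4.043) = 0.279. Its 95% CI is about 0.00 to 0.52. This does not conflict with 0.39: 0.279 is the least *observed* value that passes the test, and 0.39 is the *true* value detected with 80% power.

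**3. What each r means for one patient.** Unexplained variance is 1 − r², and the residual SD ratio is √(1 − r²). If predictor and outcome are both split at the median, the proportion correct is 1/2 + arcsin(r)/π. AUC comes from simulating 2 million bivariate normal pairs.

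| r | R2 | Unexplained variance | Residual SD / raw SD | Correct, median split | AUC |
|---|---|---|---|---|---|
| 0.279 (just significant) | 7.8% | 92% | 96% | 59% | 0.63 |
| 0.39 (design value) | 15% | 85% | 92% | 63% | 0.68 |
| 0.57 (preliminary) | 32% | 68% | 82% | 69% | 0.77 |

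For example, at r = 0.279: 1/2 + 0.2825/3.1416 = 0.590, against 0.50 by chance.

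**4. Sensitivity.**
- *Responder share.* With one third responding instead of half, AUC at r = 0.279 is 0.629 instead of 0.626. Taking the better half on the marker as predicted responders gives sensitivity 62%, specificity 56%, positive predictive value 41.5% (base rate 33%) and negative predictive value 75%.
- *Multiplicity.* With alpha split over three regions, the critical r is 0.337 (residual SD 94%, 61% correct). The conclusion does not depend on that choice.

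**5. Optimism.** If the true r is 0.28 (R2 7.8%), simulated power is about 51%, and in-sample R2 averages 15% among the significant trials, about twice the truth. Leave-one-out R2, with the leave-one-out mean as baseline, averages about 6% over all trials and 11% among the significant ones. Against the ordinary total sum of squares it averages about 2% and 8%. Its SD between trials is about 8 percentage points. So the baseline must be stated, and reporting only after a significant test brings the optimism back.

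**The case against.** The sentence is interpretive. Deleting it would change no test, estimate or sample size, and the planned correlation does match the Aim 1 hypothesis. Aim 1 also seeks insight into pathophysiology and SSRI mechanism, which a correlation can inform. This stands, and it limits the weight of the point. But the sentence is in the Statistics section and is the only stated reading of a positive Aim 1 result, so a report could rely on it.

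A reader might infer more than the documents support:

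- *That any single significant correlation counts as applicable.* The text lists three patterns across the two arms. Significance in one arm and one region is not named.
- *That 0.28 is the expected result.* It is the weakest passing value. The design value is 0.39 and the preliminary value is 0.57, so all three should be shown. The 0.28 also applies only to the specified regions at unadjusted 0.05; no threshold is given for the voxel analysis.
- *That prediction would be near chance, or that 96% of the variance is unexplained.* An AUC of 0.63 is weak but not chance. The 96% is on the SD scale; on the variance scale it is 92%.
- *That the trial cannot answer its own question.* The data will allow prediction and interaction to be estimated. What is missing is the plan to do so.

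The median split is a device for scale. The documents speak of remission, and that is why the one-third case is shown in the working.

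**Conclusion.** The point holds. Under the plan's only criterion, a result counted as applicable could carry an R2 of 8% and an AUC of about 0.63 in a specified region. At the design value these are 15% and 0.68. Even the preliminary correlation, which the protocol itself discounts, gives an AUC of about 0.77 and 69% correct. Significance at this sample size therefore shows association, with weak to moderate individual prediction, and not applicability. A correlation of the same sign in both arms does not by itself show that the marker separates ESC from placebo outcome, yet the text lists that pattern among the applicable ones.

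The critical r and the R2 values follow directly from n and alpha. AUC and proportions correct rest on bivariate normality and the responder shares shown. The point concerns the stated inference and a missing secondary analysis. It does not make the planned correlation test invalid. It is a cheap improvement.

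**What to change.** Replace the sentence in section E, Aim 1 with:

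> A significant correlation is evidence of association and identifies a candidate marker. Whatever the significance result, we will report for each specified region the cross-validated prediction of Δ HDRS in each arm (R2 with the leave-one-out mean as the stated baseline, and root-mean-square error against a model without PET), with 95% CIs, and the MRGlu-by-treatment interaction with 95% CI. No result will be described as clinically applicable without validation in new subjects.

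Both arms and the interaction are needed because prediction within ESC alone does not address whether ESC should be chosen. Cross-validation within this trial does not replace validation in new subjects.

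The cost is a short extra analysis of data already collected, with no added subjects, scans or visits, and a less favourable stated conclusion. Cross-validated estimates at n = 50 will be imprecise, which their intervals will show.
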